**A non-interventional, post-authorisation safety study of patients treated
with efgartigimod alfa**

Protocol Number: ARGX-113-PASS-2208

Version: 1.0

EU PAS Register Number: Study to be registered

Protocol Approval Date: 14 December 2023

Compound: Efgartigimod alfa (VYVGART)

Sponsor

argenx BV

The information in this document is the property of argenx and is strictly confidential. Neither the document nor the information contained herein may be reproduced or disclosed outside of argenx without the prior written consent of the company

Title	A non-interventional, post-authorisation safety study of patients treated with efgartigimod alfa.
Protocol version identifier	Version 1.0
Date of last version of protocol	
European Union (EU) Post-authorisation Study (PAS) register number	To be determined
Active substance	Efgartigimod alfa (efgartigimod)
Medicinal product	VYVGART
Product reference	H005849
Procedure number	EMA/H/C/0005849/MEA002.2
Marketing authorisation holder (MAH) & license holders	argenx BV
Joint post-authorisation safety study (PASS)	No
Research question and objectives	
A non-interventional 10-year Post-Authorization Safety Study (PASS) in a post-marketing setting comparing cohorts of patients with gMG treated with efgartigimod to those treated with other MG medication, in order to estimate the incidence rates of serious infection and other safety events.
 
Primary Objective
 
 To evaluate the overall long-term safety of efgartigimod including the occurrence of serious infections in generalized myasthenia gravis (gMG) patients treated with efgartigimod compared to gMG patients not exposed to efgartigimod. 
Exploratory Objectives
 
 To evaluate the safety of efgartigimod in immunocompromised patients To evaluate the safety of efgartigimod administered to patients treated with monoclonal antibodies To evaluate the safety of efgartigimod in patients receiving live/attenuated vaccine To evaluate the safety of efgartigimod in patients with moderate to severe renal impairment
Regions and countries of study	Europe & United States (US)
Author	argenx BV

Marketing Authorization and License Holders

MAH & License holders	argenx BV [name]
MAH contact person	Mrs. [REDACTED]

Sponsor Approval

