9. RESEARCH METHODS

9.1 Study Design

This is a non-interventional, prospective, post authorisation safety study.

Patients with gMG who are expected to start treatment with efgartigimod at enrolment or are within their first cycle of efgartigimod at enrolment will be eligible to enrol into the efgartigimod cohort. Patients with gMG who have not been exposed to efgartigimod and for whom it is not planned to start treatment with efgartigimod at enrolment will be eligible to enrol into the non-efgartigimod cohort. It is anticipated that 340 patients will be enrolled in each cohort.

Patients will be treated and observed according to normal clinical practice. Participation in this study does not limit the physicians` clinical decision making as to the most appropriate treatment for the patient during the course of the study. No visits or investigations outside of normal clinical practice will be required. The enrolled patients will be followed prospectively until end of study participation, loss to follow up, consent withdrawal, or death, whichever comes first. All adverse events (AEs) will be collected throughout the duration of the study.

Enrolment of patients will be over a 5-year period. The follow up of patients will continue for 5 years from the time the last patient has been enrolled. Patients will be followed regardless of whether they continue or discontinue efgartigimod. Assuming a 5-year enrolment period this will allow for a maximum of 10 years of follow-up and a minimum of 5 years. A patient will be considered to be an efgartigimod exposed patient if he/she has received at least one dose of efgartigimod.

In order to minimise heterogeneity between the two cohorts, patients in the efgartigimod cohort will be matched at enrollment with a patient in the non-efgartigimod cohort for the following criteria:

- Age (\pm 5 years)
- Myasthenia Gravis -Activities of Daily Living (MG-ADL) score (0-5, 5-9, and >9) ([Wolfe, 1999](#))
- Region (within EU and within US)

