9.2 Setting

This study will be conducted in the EU, the United Kingdom (UK) and the US at clinics which manage patients with gMG. The number of sites and countries is dependent upon market access and market launch. It is anticipated that in addition to the US, countries will include, but not be limited to, Germany, France, Italy and UK. If feasible, data may also be collected from the Deutsches Myasthenie Register (MyaReg) which is a German MG registry.

All eligible patients from each participating site will be invited to participate in the study in order to minimise selection bias. For eligible patients who do not enrol, the reason for non-enrolment will be collected by the site and maintained in a non-enrolment log. At the end of the enrolment period , aggregate, non-identifiable data from the non-enrolment log will be provided to the sponsor.

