9.2.1 Selection of Study Population

Patients with gMG who are expected to start treatment with efgartigimod at enrolment or are within their first cycle of efgartigimod at enrolment will be eligible to enrol into the efgartigimod cohort. Patients with gMG who have not been exposed to efgartigimod and for whom it is not planned to start

treatment with efgartigimod at enrolment will be eligible to enrol into the non-efgartigimod cohort.

Physicians participating in the study will be instructed to invite all patients who meet study eligibility criteria to enrol until the enrolment period is closed.

Inclusion Criteria (efgartigimod cohort)

1. Patients diagnosed with gMG who are expected to start commercial efgartigimod at enrolment or who are within their first cycle of efgartigimod at enrolment
2. Have provided appropriate written informed consent

Inclusion Criteria (non-efgartigimod cohort)

3. Patients diagnosed with gMG who have not been exposed to efgartigimod and for whom it is not planned to start treatment with efgartigimod at enrolment
4. Have provided appropriate written informed consent

Exclusion Criteria

None

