gMG treatments at or following enrollment (excluding efgartigimod)	
 Drug name, dose, start and stop dates 
 Acetylcholinesterase inhibitors Corticosteroids Other Immunosuppressants (specify) Monoclonal antibodies (specify) Plasmapheresis/plasma exchange acute Plasmapheresis/plasma exchange chronic IVIg therapy acute IVIg therapy chronic Other 	✓	✓

Category	Variables	Baseline	Follow up
Efgartigimod treatment	
 • Date of administration • Reason for interruption during cycle of treatment • Reason for permanent discontinuation whilst on study 	✓	✓
Other comedications at or following enrollment for conditions other than gMG	
 • Drug name, start and stop dates • Indication 	✓	✓
Live/attenuated vaccinations 2 months prior to enrollment to 2 months after last Vyvgart dose	
 • Live/attenuated vaccine 
 ○ Vaccine ○ Date 	✓	✓
Adverse Events (AEs)/Serious Adverse Events (SAEs)	
 • AEs, SAEs 		✓
Events of interest	See Table 2		✓

*All variables will be collected ONLY if available as part of routine clinical practice

A patient will be considered to be an efgartigimod exposed patient if he/she has received at least one dose of efgartigimod.

Additionally, taking into account the variable follow up time and time interval between cycles, the following will be measured for efgartigimod:

- Number of administrations per year
- Total duration of the exposure
- Total number of administrations

The exposure time window of efgartigimod is 56 days +/-3 days after the last dose.

Events of interest in this study will be pre-specified as per [Table 2](#) below.

Table 2: Pre-specified events of interest

Event of interest	Definition	Measurement
Serious infection	Any serious adverse event coded to the Medical Dictionary for Regulatory Activities (MedDRA) System Organ Class (SOC) of Infection and Infestation. See Section 11 for definition of Serious.	Proportion of patients who report serious infections during the course of the study in the efgartigimod treated cohort compared to the non-efgartigimod cohort. Incidence rate of serious infections per patient-years exposed in the efgartigimod treated cohort compared to the non-efgartigimod cohort.

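### The matching rule is ill-defined for some patients (MG-ADL of 5, UK sites, no recorded score), and the analysis keeps every enrolled patient whether matched or not

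*Protocol*

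**What the plan says.** The abstract and section 9.1 both state that patients in the efgartigimod cohort are matched at enrolment with a patient in the other cohort, to reduce heterogeneity. The criteria are age within 5 years, "Myasthenia Gravis -Activities of Daily Living (MG-ADL) score (0-5, 5-9, and >9") and "Region (within EU and within US").

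Other sections bear on whether that rule can be applied:

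- **Setting (9.2):** "This study will be conducted in the EU, the United Kingdom (UK) and the US at clinics which manage patients with gMG". Besides the US, "countries will include, but not be limited to, Germany, France, Italy and UK". The title-page summary table gives the study regions as "Europe & United States (US").
- **Data (9.2.3, 9.3):** no visit, test or assessment is mandatory. The footnote to Table 1 says "All variables will be collected ONLY if available as part of routine clinical practice". MG-ADL is one of those variables.
- **Enrolment (9.2.1):** there are no exclusion criteria, and neither inclusion list asks for an MG-ADL score. Physicians are "instructed to invite all patients who meet study eligibility criteria to enrol until the enrolment period is closed".
- **Analysis (9.7):** all analyses use the Safety Population, which is every enrolled comparator plus every enrolled efgartigimod patient with at least one dose. The logistic and Cox base models contain treatment group and country. Balance of the baseline measures, including the matching factors, is assessed. Imbalanced measures judged clinically to be confounders are then added, or a propensity score is used if there are many.

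**The concern.** Section 9.9 expects the more severe patients to receive efgartigimod, so the severity comparison is where this study is most exposed to confounding. Matching is the only control applied at the design stage, and MG-ADL is its only severity factor. If some patients have two possible bands, or none, sites may pair them inconsistently or leave them unpaired. They still enter the analysis, and the base models do not adjust for severity unless an imbalance is detected and judged to matter.

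Timing matters too. Matching takes place at enrolment, over five years. A statistical analysis plan can specify adjustment, but it cannot go back and decide which comparators should have been recruited. The bands and region levels are also written into the protocol, so they are stated badly and not simply left for later.

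**Working it through.** **1. The bands.** Testing integer scores against 0-5, 5-9 and >9:

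- 0 to 4: first band only.
- 5: first and second bands.
- 6 to 9: second band only.
- 10 and above: third band only.

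One score is doubly assigned and none is unassigned. A patient scoring 5 may be paired with anyone from 0 to 9, but the gap within a pair is at most 5 − 0 = 5 points on one side and 9 − 5 = 4 on the other. A 0-5 band alone already allows a 5-point gap. With 0-4 and 5-9 the largest gap within either band is 4, so exclusive bands shorten the worst such pair by one point. Their main benefit is that every recorded score gets one band.

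**2. The regions.**

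| Place | Regions named |
|---|---|
| Title-page table | Europe, US |
| Section 9.2 | EU, UK, US |
| Matching rule (abstract, 9.1) | EU, US |

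The UK is expected to take part but has no level in the matching rule unless EU is read as Europe.

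**3. Missing scores.** MG-ADL appears at baseline in Table 1, subject to the routine-practice footnote. Section 9.3 itself warns of missing data. No level is given for a patient without a score. The handling in section 9.7 (mean for a continuous covariate, a missing category for a categorical one) applies to model covariates, not to the match.

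**4. The link to analysis.** The Safety Population definition has no condition that a match exists, and no section says what happens when none is found.

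**5. The protocol's own figures.** Section 9.5 does not use the matching, and its figures reproduce:

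- Inflation for drop-out: 270 / (1 − 0.20) = 337.5, so 338, against 340 stated.
- Power for 20% v 31% with 270 per arm, two-sided 0.05: SE = √[(0.20×0.80 + 0.31×0.69)/270] = √(0.3739/270) = 0.0372; 0.11/0.0372 − 1.96 ≈ 1.00, giving 84.0% (83.7% with a pooled variance), against 84% stated.

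Neither changes under the fix.

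**6. How many patients.** The documents give none of the shares, so this is illustration only. With a = share scoring 5, u = share from the UK and m = share without a score, assumed independent, the fraction without a unique stratum is 1 − (1−a)(1−u)(1−m).

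| Assumed a, u, m | Fraction | Of 340 |
|---|---|---|
| 5%, 5%, 5% | 1 − 0.95×0.95×0.95 = 14% | 48 |
| 12%, 20%, 30% | 1 − 0.88×0.80×0.70 = 51% | 172 |
| 5%, UK placed in Europe, 5% | 1 − 0.95×0.95 = 10% | 33 |
| 12%, UK placed in Europe, 30% | 1 − 0.88×0.70 = 38% | 131 |
| Overlap alone, 5% to 10% | 5% to 10% | 17 to 34 |

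**The case against.** The strongest reply is that the rule works for most of what it covers. EU or US patients with a recorded score other than 5 have exactly one stratum, and a score of 5 is ambiguous but not unmatchable. That stands. A reader might infer that the rule cannot be run at all, or that the analysed cohorts will be unmatched. The documents do not support this: section 9.1 commits to matching, and the gaps concern identifiable groups. A reader might also infer from the overlap that pairs can differ by 9 points; step 1 of the working shows the limit is 5.

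Second, the UK limb is the weakest. The title-page wording makes it plausible that EU was meant as Europe. This is a mismatch to reconcile, not proof that UK patients are excluded from matching.

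Third, section 9.7 checks balance on the matching factors and offers covariate adjustment or a propensity score, and country is already in both base models. This is real mitigation, so matching is not the only control on confounding. It is conditional, however, and mean imputation or a missing category weakens severity adjustment for the same unscored patients whom the match could not place.

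Fourth, section 9.9 says variables were aligned as far as possible with normal practice, so missing scores may be few, and handling of missing data is partly deferred to the statistical analysis plan. That is fair for the analysis. It does not help a matching step carried out at enrolment.

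**Conclusion.** The point holds for part of the cohort. The overlap at 5 is certain and appears in both the abstract and section 9.1. The absence of any level for unscored patients follows directly from the Table 1 footnote and the eligibility criteria. The UK gap depends on reading EU literally. That unmatched patients are analysed, under base models without age or MG-ADL, is plain from section 9.7.

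The size cannot be fixed from the documents. The 14% to 51% range rests wholly on assumed, independent shares, and the overlap by itself is modest. Nor do the documents show that any bias will result; they show that the design control against an imbalance the protocol expects is incompletely specified. Sample size, precision and power are unaffected. The change should be made before the first patient is enrolled.

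**What to change.** 1. In the abstract and section 9.1, make the MG-ADL bands mutually exclusive, for example 0-4, 5-9 and >9.
2. Define region as Europe (EU plus UK) or US, and use the same wording on the title page, in the abstract and in sections 9.1 and 9.2.
3. Give patients without an MG-ADL score an explicit matching level: MGFA class where available, otherwise unknown. MGFA class falls under the same routine-practice footnote, so the unknown level is needed as well.
4. In section 9.7, always include age, MG-ADL, and region or country in the logistic and Cox base models, instead of adding age and MG-ADL only when imbalanced.
5. State how enrolled patients without a match are treated, and reconcile matching at enrolment with the instruction to invite every eligible patient.

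Opening comparator enrolment by stratum is one option for item 5, not a required change. It would leave eligible comparators in closed strata unenrolled, which trades against the protocol's aim of limiting selection bias by inviting all.

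The cost is a few lines on the title page, in the abstract and in sections 9.1, 9.2, 9.2.1 and 9.7, with stratum tracking in the EDC system if the capped option is chosen. The added covariates cost almost nothing in the models.

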9.2 Setting

This study will be conducted in the EU, the United Kingdom (UK) and the US at clinics which manage patients with gMG. The number of sites and countries is dependent upon market access and market launch. It is anticipated that in addition to the US, countries will include, but not be limited to, Germany, France, Italy and UK. If feasible, data may also be collected from the Deutsches Myasthenie Register (MyaReg) which is a German MG registry.

All eligible patients from each participating site will be invited to participate in the study in order to minimise selection bias. For eligible patients who do not enrol, the reason for non-enrolment will be collected by the site and maintained in a non-enrolment log. At the end of the enrolment period , aggregate, non-identifiable data from the non-enrolment log will be provided to the sponsor.

9.2.1 Selection of Study Population

Patients with gMG who are expected to start treatment with efgartigimod at enrolment or are within their first cycle of efgartigimod at enrolment will be eligible to enrol into the efgartigimod cohort. Patients with gMG who have not been exposed to efgartigimod and for whom it is not planned to start

treatment with efgartigimod at enrolment will be eligible to enrol into the non-efgartigimod cohort.

Physicians participating in the study will be instructed to invite all patients who meet study eligibility criteria to enrol until the enrolment period is closed.

Inclusion Criteria (efgartigimod cohort)

1. Patients diagnosed with gMG who are expected to start commercial efgartigimod at enrolment or who are within their first cycle of efgartigimod at enrolment
2. Have provided appropriate written informed consent

Inclusion Criteria (non-efgartigimod cohort)

3. Patients diagnosed with gMG who have not been exposed to efgartigimod and for whom it is not planned to start treatment with efgartigimod at enrolment
4. Have provided appropriate written informed consent

Exclusion Criteria

None

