The study design includes an efgartigimod cohort and a comparator cohort of non-efgartigimod treated patients. The duration of the study is a maximum of 10 years (5 years of enrolment and 5 years of follow up). Over this time period, standard of care for the treatment of gMG is likely to evolve with the introduction of new medicinal products such as ultomiris (recently approved) and rozanolixizumab and zilucoplan (currently under review with an approval expected by end of 2023) and the potential for patients to switch treatments during this time. The comparator group, and indeed the efgartigimod group, will therefore be heterogenous in terms of treatments, thus limiting the interpretability of the results.

Furthermore, in countries where efgartigimod is marketed, it is likely that the efgartigimod cohort and the comparator cohort will differ in terms of disease severity with the more severe patients receiving efgartigimod. Thus, there will be an inherent selection bias. This could be solved by recruiting the comparator patients from countries where efgartigimod is not marketed. However, this will introduce further biases in terms of differing standards of care.

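### Matching at enrolment sets no enrolment-date criterion while all eligible patients are invited, so comparators can enter earlier than efgartigimod starters, which the crude proportion and the logistic base model do not account for

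*Protocol*

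**What the plan says.** **Recruitment.** Section 9.2 states: "All eligible patients from each participating site will be invited to participate in the study in order to minimise selection bias". Section 9.2.1 repeats this as an instruction to physicians, who "will be instructed to invite all patients who meet study eligibility criteria to enrol until the enrolment period is closed". Neither section sets a pace, cap or order by cohort.

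**Eligibility.** The comparator criterion in 9.2.1 is "Patients diagnosed with gMG who have not been exposed to efgartigimod and for whom it is not planned to start" efgartigimod at enrolment. No new treatment, recent diagnosis or other index event is required. The efgartigimod cohort takes only patients about to start or still in their first cycle.

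**Size and matching.** Section 9.1 says "It is anticipated that 340 patients will be enrolled in each cohort" and that "patients in the efgartigimod cohort will be matched at enrollment with a patient in the non-efgartigimod cohort". The criteria, repeated in the abstract, are age within 5 years, MG-ADL band and region. Enrolment date is not among them.

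**Follow-up.** Enrolment lasts 5 years and data collection closes at one date, so follow-up is 5 to 10 years depending on entry (9.1, 9.5).

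**Analysis.** Table 2 compares both the proportion of patients with serious infection over the study and a rate per patient-years. Section 9.7 adds person-year rates and two base models: a logistic regression and a Cox regression, each with treatment group and country as covariates. The Cox model is there to handle varied follow-up. Imbalanced baseline measures may be added as covariates or handled by a propensity score.

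**The concern.** The two cohorts become eligible in different ways. A clinic's existing efgartigimod-naive patients can all be invited on the day the site opens. Starters arrive one at a time over the enrolment period. A site that follows the invite-all instruction literally will tend to enrol comparators first, and nothing in the matching criteria prevents that.

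Two consequences follow if it happens:

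- **Longer comparator follow-up.** A cumulative proportion rises with time at risk. The crude proportion and the logistic model would then show more serious infections among comparators even if the drug had no effect. In a safety study this is the harmful direction, because it can hide a real excess.
- **Earlier comparator calendar time.** Section 9.9 expects that "standard of care for the treatment of gMG is likely to evolve with the introduction of new medicinal products". A difference in enrolment period would carry some of that change into every between-cohort comparison, including the Cox model.

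Once comparators have been enrolled early, the analysis can adjust for their entry dates but cannot change them. The matching rule therefore belongs in the protocol.

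**Working it through.** **The plan's own figure.** Section 9.5 gives 84% power for 20% versus 31% with 270 per arm, two-sided alpha 0.05, normal approximation.
- Unpooled: SE = sqrt[(0.20×0.80 + 0.31×0.69)/270] = 0.0372; z = 0.11/0.0372 − 1.96 = 1.00; power 84.0%.
- Pooled variance under the null gives 83.7%.

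Table 4 is sound on its inputs. It takes one proportion per arm, which implicitly assumes equal follow-up.

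**Inputs from the protocol.** 20% serious-infection proportion and 340 per cohort (9.5); enrolment over years 0-5 and a common close at year 10 (section 6, 9.1).

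**Assumptions, not in the protocol.** Constant hazard, the same in both cohorts; 20% reached at 7.5 years, the mean follow-up if entry is even over years 0-5; no drop-out; uniform entry within each window.

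**Formula.** Hazard h = −ln(0.8)/7.5 = 0.02975 per year. For entry spread evenly from time a to time b, the expected proportion is

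P(a,b) = 1 − [exp(−h(10−b)) − exp(−h(10−a))] / [h(b−a)]

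- Starters, 0-5: 1 − (0.8618 − 0.7427)/(0.02975×5) = **19.9%**, mean follow-up 7.5 years
- Comparators, 0-1: 1 − (0.7651 − 0.7427)/(0.02975×1) = **24.6%**, 9.5 years
- Comparators, 0-2: 1 − (0.7882 − 0.7427)/(0.02975×2) = **23.5%**, 9.0 years
- Comparators, 0-3: 1 − (0.8120 − 0.7427)/(0.02975×3) = **22.3%**, 8.5 years

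(Exponentials are shown to four places; results use full precision.)

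| Comparator entry | Spurious gap | Odds ratio, efgartigimod vs comparator | Two-proportion test rejects, no true effect, n=340 |
|---|---|---|---|
| 0-1 | 4.7 points | 0.76 | 31% |
| 0-2 | 3.6 points | 0.81 | 20% |
| 0-3 | 2.4 points | 0.87 | 12% |
| 0-5 (same as starters) | 0 | 1.00 | 5% |

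**Drop-out.** Add drop-out at a constant rate reaching 20% by 7.5 years, and reset the hazard so that starters show 20.0%. Comparators then show 24.1%, 23.1% and 22.1%. The gaps are 4.1, 3.1 and 2.1 points, and false rejection is 25%, 17% and 10%.

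**Effect on power.** Take a true excess of 20% versus 30% at equal follow-up (hazard ratio about 1.6), with hazards set so that entry over years 0-5 gives exactly those values and no drop-out. At 330 per arm the crude comparison has 84.5% power (Table 4: 85%). It falls to 33%, 46% or 60% when comparators enter over years 0-1, 0-2 or 0-3.

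**Analyses not affected by follow-up length.** Under a constant hazard, events divided by person-years estimates h whatever the entry date, and the Cox model compares patients at equal time since entry. Neither is biased by unequal follow-up alone.

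**The case against.** Several points on the other side have force.

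- **Matching at enrolment may already mean concurrent pairing.** This is a plausible reading of 9.1, and it would pace comparators to starters. A reader might infer that the two rules flatly contradict each other, or that comparators will certainly fill early. The text supports neither. It supports an ambiguity that permits early filling.
- **The protocol handles follow-up length elsewhere.** The research question is about incidence rates, Table 2 pairs each proportion with a rate, and the Cox model is included for this purpose. It would be wrong to say the whole comparison is biased by unequal follow-up. The gaps above apply to the crude proportion and the logistic model only. These remain stated analyses of the primary objective.
- **Dependence on market launch does not delay starters alone.** Section 9.2 ties the number of sites and countries to launch, which affects when both cohorts open. Staggered opening makes the 0-1 scenario an extreme, and the country term absorbs part of any between-country timing difference. It does not remove a within-site gap.
- **The calendar effect is limited and not quantified.** Without drop-out, everyone is observed over years 5-10. That shared window holds 5/9.5 = 53% of comparator person-time in the most extreme scenario and 5/7.5 = 67% of starter person-time. Section 9.9 already discloses evolving care.
- **Covariates may be added.** Section 9.7 allows this for imbalanced baseline measures, namely the matching factors and other demographic and disease characteristics. Enrolment date is not named.

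A reader might also set the gaps against a 10-point increase as the design target. Section 9.5 sizes the study on a 5% half-width; power is supplementary.

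**Conclusion.** The point holds as a risk that the design permits. The protocol does not say whether matched pairs must enrol at about the same time, and the eligibility rules let comparators enter earlier. If they do, the crude serious-infection proportion and the logistic base model are biased in favour of efgartigimod. The bias is about 2.4 to 4.7 points without drop-out and 2.1 to 4.1 points with it, when all comparators enter within the first three years to the first year and starters enter evenly over five.

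These sizes rest on the assumed accrual patterns and a constant, equal hazard. If comparators accrue over the same years as starters, the bias is zero. Person-year rates and the Cox model are unaffected by follow-up length. They remain open to a difference in enrolment period, for which neither base model has a term; the size of that effect cannot be derived from the protocol. The sample-size and power tables contain no error on this account.

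**What to change.** 1. In the abstract and 9.1, add enrolment date to the matching criteria, for example within ±6 months of the starter's enrolment.
2. In 9.2 and 9.2.1, reconcile this with the invite-all instruction by stating when comparators are approached and what happens to those enrolled without a starter in their window. Inviting all eligible patients is the protocol's own safeguard against selection bias (9.2, 9.9). Replacing it with a rule such as taking the next clinic attendee would weaken that safeguard and should not be the main remedy.
3. In 9.7, include enrolment year in both base models.
4. In 9.7, name the Cox and person-year results as the lead between-cohort comparison, with the crude proportion and logistic model as supporting.

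The cost is protocol wording, a tracker in the EDC system to monitor open pairs, and one added model term. The downside is that some pairs take longer to find and comparator accrual becomes partly tied to the pace of starters.
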